## CONTINUUM PROTOCOL SUMMARY

Title:	
CONTINUUM
 
CONTINUous Infra-Inguinal Stenting Using the Bard® LifeStent® VascUlar Stent SystemS
								
Objectives:	
The objective of this study is to collect post-market confirmatory evidence of the safety and effectiveness of the Bard® LifeStent® Vascular Stent System, the LifeStent® XL Vascular Stent System, and the LifeStent® SOLO™ system (together the “LifeStent® Vascular Stent System”).
								
Design:	
This study is a prospective, multi-center, single-arm, non-randomized study enrolling subjects with lifestyle-limiting claudication or ischemic rest pain attributable to lesion(s) (stenosed, occluded, restenosed, or re-occluded) in the infra-inguinal segment (superficial femoral artery (SFA) and/or proximal popliteal artery) that are amenable to treatment by percutaneous transluminal angioplasty (PTA) and stenting. Investigators should select an appropriately sized device(s) to treat subjects with target lesion(s) up to 240 mm.
 
Clinical follow-up for all subjects will be performed at hospital discharge, 30-days and 12-, 24-, and 36-months post-procedure.
								
Sponsor:	
Bard Peripheral Vascular, Inc. (“Bard”)          [name]          [name] USA
								
Devices:	
Bard® LifeStent® Vascular Stent Systems:
 
 
 Stent Diameters:	6.0 and 7.0 mm	
 
 Stent Lengths: LifeStent®	20, 30, 40, 60 and 80 mm	
 
 LifeStent® XL	100, 120, 150 and 170 mm	
 
 LifeStent® SOLO™	20, 30, 40, 60, 80, 100, 120, 150, 170, and 200 mm	
 
	Stent Diameters:	6.0 and 7.0 mm	Stent Lengths: LifeStent®	20, 30, 40, 60 and 80 mm	LifeStent® XL	100, 120, 150 and 170 mm	LifeStent® SOLO™	20, 30, 40, 60, 80, 100, 120, 150, 170, and 200 mm
Stent Diameters:	6.0 and 7.0 mm								
Stent Lengths: LifeStent®	20, 30, 40, 60 and 80 mm								
LifeStent® XL	100, 120, 150 and 170 mm								
LifeStent® SOLO™	20, 30, 40, 60, 80, 100, 120, 150, 170, and 200 mm								
Enrollment:	
A minimum of two-hundred thirty-four (234) subjects in a non-randomized fashion.
 
At least 64 subjects with target lesion lengths < 160 mm and at least 64 subjects with target lesion lengths > 160 mm and ≤ 240 mm will be enrolled. In addition to the original 170 subjects required, at least 64 additional subjects treated with the 200 mm LifeStent® will be enrolled.
								

Investigational Sites:	Up to thirty-five (35) investigational sites (“sites”) will be utilized for this study.
Procedures:	Subjects will undergo a clinical evaluation at baseline/screening (prior to index procedure), prior to hospital discharge, 30-days and 12-, 24- and 36-months post-procedure.
Medications:	
Pre-Procedure: Subjects are to receive a minimum of 81 mg of aspirin (ASA) orally per day and a minimum of 75 mg of Clopidogrel orally per day, beginning the day of the index procedure, and no later than 2 hours following the index procedure.
 
Post-Procedure: Subjects are to continue to receive a minimum of 81 mg of ASA orally per day for a recommended minimum of 6 months, and a minimum of 75 mg of Clopidogrel orally per day for a minimum of 12 weeks.

Study Population:	
The study population will be comprised of subjects who present with lifestyle-limiting claudication or ischemic rest pain and are candidates for PTA and stenting.
 
Prior to enrollment, each subject will have a diagnostic assessment that enables qualification of the target lesion(s). Subjects with lesion(s) in the infra-inguinal segment (SFA and/or proximal popliteal arteries) will be considered for enrollment. The reference vessel diameter must be <math>\geq 4.0</math> mm and <math>\leq 6.5</math> mm.

Primary Endpoints:	
Safety (Death):
 

– Freedom from occurrence of death at 30-days and 12-months post-index procedure.

 
Effectiveness (Device Success):
 

– Freedom from acute delivery failure; and,

– Primary Target Lesion Patency (TLP) at 12-months post-index procedure.

Secondary Endpoints	
	

– Freedom from Target Lesion Revascularization (TLR) and/or Target Vessel Revascularization (TVR) at 12-months post-index procedure.

– Secondary Device Success (compared to RESILIENT LifeStent®).

– Primary Safety of the Target Lesion Lengths > 160 mm subgroup compared to the Target Lesions treated with the 200 mm LifeStent® subgroup.

– Primary Safety of the following subgroups: 1) Target Lesion Lengths ≤ 160 mm, 2) Target Lesion Lengths > 160 mm and ≤ 240 mm, and 3) Target Lesions treated with the 200 mm LifeStent®.

– Primary Effectiveness of the Target Lesion Lengths > 160 mm subgroup compared to the Target Lesions treated with the 200 mm LifeStent® subgroup.

– Primary Effectiveness of the following subgroups: 1) Target Lesion Lengths ≤ 160 mm, 2) Target Lesion Lengths > 160 mm and ≤ 240 mm, and 3) Target Lesions treated with the 200 mm LifeStent®.

– Freedom from Fracture (FFF) at 12- and 24-months post-index procedure.

– Primary TLP (Sustained and Expanded) for Target Lesion Lengths > 160 mm at 12-, 24- and 36-months post-index procedure.

– Freedom from TLR and/or TVR for Target Lesion Lengths > 160 mm at 12-, 24-, and 36-months post-index procedure.

– Secondary Safety defined as freedom from death (excluding 30-days and 12-months post-index procedure), stroke, myocardial infarction (MI), emergent surgical revascularization, significant distal embolization in target limb, target limb major amputation, and thrombosis of target vessel at 30-days and 12-, 24-, and 36-months post-index procedure.

– Acute Technical Success defined as successful deployment of the stent to the intended location.

– Acute Lesion Success defined as attainment of ≤ 30% residual stenosis of the target lesion using any percutaneous method and/or non-investigational device (i.e., post-dilatation).

– Acute Procedure Success defined as lesion success and no periprocedural complications (death, stroke, MI, emergent surgical revascularization, significant distal embolization in target limb, and thrombosis of target vessel).

– Sustained Freedom from TLR and/or TVR at 24- and 36-months post-index procedure

– Sustained Hemodynamic Success defined as sustained improvement of Ankle-Brachial Index (ABI) from baseline value of ≥ 0.15 at 30-days and 12-, 24-, and 36-months post-index procedure without the need for repeated TLR in surviving subjects.

– Sustained Clinical Success defined as sustained cumulative improvement from baseline value of ≥ 1 category according to Rutherford et al at 30-days and 12-, 24-, and 36-months post-index procedure without the need for repeated TLR in surviving subjects.


	
 
– Sustained TLP at 24- and 36-months post-index procedure corresponding to PSR < 2.5.
 
– Expanded TLP at 12-, 24- and 36-months post-index procedure corresponding to PSR < 3.0.
 
– Cumulative (primary-assisted and secondary) TLP at 12-, 24-, and 36-months post-index procedure corresponding to PSR < 2.5, and PSR < 3.0.
 
– Quality of Life as assessed by Walking Impairment Questionnaire (WIQ) at baseline, 30-days and 12-, 24- and 36-months post-index procedure.
 

Principal Investigators:	
[name]          Aurora St. Luke’s Medical Center          [name]          [name]
 
[name]          The Cooper Health System          [name]          [name]

Clinical Affairs:	
[name]          Bard Peripheral Vascular, Inc.          [name]          [name] USA

Contract Research Organization/Data Coordinator Center	
[name]          Project Manager          Novella Clinical, Inc.          [name]          [name]          [contact]          [contact]          Email: [contact]

Angiographic/X-Ray Core Lab:	
[name]          Cardiovascular Research Foundation          [name]          [name]          [contact]

Duplex Ultrasound Core Lab:	
[name], DO, FACP, FACC          VasCore          [name]          [name]          [contact]

---

## Statistical Analysis Plan

### 1. Study Endpoints

Primary and two secondary effectiveness endpoints (i.e., freedom from TLR/TVR through 12-months post-index procedure, and secondary device success) will be compared to the RESILIENT trial results (historical control).

#### A. Primary Safety Endpoint

The primary safety endpoint of the study is defined as: Freedom from occurrence of death at 30-days and 12-months post-index procedure.

#### B. Primary Effectiveness Endpoint

The primary effectiveness endpoint of the study, device success, will collectively measure both acute and chronic effectiveness.

Acute effectiveness is defined as: Successful delivery of the stent to the intended site with the post-deployment stent length being within 10% of the pre-deployment stent length.

Chronic effectiveness is defined as: Primary Target Lesion Patency (TLP) at 12-months post-index procedure, as measured by DUS. TLP is defined as the interval following the index procedure until a DUS assessment indicates that the target lesion(s) is no longer patent; that is, the treated segment has a peak systolic velocity ratio (PSR)  $\geq 2.5$ . PSR is determined by comparing velocities within the treated segment to the proximal normal arterial segment. In this study, a  $> 50\%$  stenosis is defined as a PSR of  $\geq 2.5$ .

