#### C. Secondary Endpoints

1. **Freedom from TLR and/or TVR** through 12-months post-index procedure. TLR is defined as the interval following the index procedure until the first revascularization procedure (e.g. PTA, cryoplasty, etc.) of the target lesion. TVR is defined as the interval following the index procedure until the first revascularization procedure (e.g. PTA, stenting, surgical bypass, etc.) in the target vessel.
2. **Secondary Device Success** (compared to RESILIENT LifeStent®).
3. **Primary Safety** (freedom from occurrence of death at 30-days and 12-months post-index procedure) of the *Target Lesion Lengths > 160 mm* subgroup compared to the *Target Lesions treated with the 200 mm LifeStent®* subgroup.
4. **Primary Safety** (freedom from occurrence of death at 30-days and 12-months post-index procedure) of the following subgroups: 1) *Target Lesion Lengths  $\leq 160$  mm*, 2) *Target Lesion Lengths > 160 mm and  $\leq 240$  mm*, and 3) *Target Lesions treated with the 200 mm LifeStent®*.
5. **Primary Effectiveness** (Device Success) of *Target Lesion Lengths > 160 mm* subgroup compared to the *Target Lesions treated with the 200 mm LifeStent®* subgroup.

6. **Primary Effectiveness** (Device Success) of the following subgroups: 1) *Target Lesion Lengths  $\leq 160$  mm*, 2) *Target Lesion Lengths  $> 160$  mm and  $\leq 240$  mm*, and 3) *Target Lesions treated with the 200 mm LifeStent®*.
7. **Freedom from Fracture** (FFF) at 12- and 24-months post-index procedure.
8. **Primary TLP (Sustained and Expanded) for Target Lesion Lengths  $> 160$  mm** at 12, 24- and 36-months post-index procedure corresponding to PSR values of  $< 2.0$ ,  $< 2.5$ , and  $< 3.0$ .
9. **Freedom from TLR and/or TVR for Target Lesion Lengths  $> 160$  mm** at 12-, 24-, and 36-months post-index procedure.
10. **Secondary Safety** defined as freedom from death (excluding 30-days and 12-months post-index procedure), stroke, MI, emergent surgical revascularization, significant distal embolization in target limb, target limb major amputation, and thrombosis of target vessel at 30-days and 12-, 24-, and 36-months post-index procedure.
11. **Acute Technical Success** defined as successful deployment of the stent to the intended location.
12. **Acute Lesion Success** defined as attainment of  $\leq 30\%$  residual stenosis of the target lesion using any percutaneous method and/or non-investigational device (i.e., post-dilatation).

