13. **Acute Procedure Success** defined as lesion success and no peri-procedural complications (death, stroke, MI, emergent surgical revascularization, significant distal embolization in target limb, and thrombosis of target vessel).
14. **Sustained Freedom from TLR and/or TVR** at 24- and 36-months post-index procedure.
15. **Sustained Hemodynamic Success** defined as sustained improvement of Ankle-Brachial Index (ABI) from baseline value of  $\geq 0.15$  at 30-days and 12-, 24-, and 36-months post-index procedure without the need for repeated TLR in surviving subjects.
16. **Sustained Clinical Success** defined as sustained cumulative improvement from baseline value of  $\geq 1$  category according to Rutherford et al. at 30-days and 12-, 24-, and 36-months post-index procedure without the need for repeated TLR in surviving subjects.
17. **Sustained TLP** at 24- and 36-months post-index procedure corresponding to PSR  $< 2.5$ .
18. **Expanded TLP** at 12-, 24- and 36-months post-index procedure corresponding to PSR  $< 3.0$ .
19. **Cumulative (primary-assisted and secondary) TLP** at 12-, 24-, and 36-months post-index procedure corresponding to PSR  $< 2.5$  and PSR  $< 3.0$ .
20. **Quality of Life** as assessed by Walking Impairment Questionnaire (WIQ) at baseline, 30-days and 12-, 24- and 36-months post-index procedure.

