8. The censoring rate through 12-months post-index procedure will be 15%.

According to PASS 2008 (using the Cox's survival analysis module), the sample size required for 80% power is 252 subjects with just over 50% in one of the groups. The RESILIENT LifeStent® group has 112, so implanting 140 (56%) or more CONTINUUM LifeStent® subjects will provide at least 80% power. When this is inflated to accommodate 15% censoring through 12-months post-index procedure, the CONTINUUM sample size is 165 subjects. This sample size estimate demonstrates that secondary effectiveness (device success) is the sample-size driver for this study.

However, a minimum of 170 subjects are required to be enrolled as originally agreed upon and referenced in the FDA Post-Market Approval (PMA) Approval Order of the Bard® LifeStent® Vascular Stent (P070014). The secondary endpoint, "Device Success" demonstrated that 165 subjects are necessary to power this endpoint, including adjusting for censoring; this is very close to the 170 subjects initially stipulated by FDA. In addition to this requirement, at least 64 additional subjects treated with the 200 mm LifeStent® will be enrolled (including adjustment for censoring), which results in a minimum enrollment of 234 subjects in the study.

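### Primary target lesion patency ends only on a failing duplex scan, so a lesion re-treated before 12 months can still be scored primary-patent

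*Combined protocol and SAP*

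**What the plan says.** - **SAP 1.B, Primary Effectiveness Endpoint.** Device success combines acute delivery with primary TLP at 12 months, measured by DUS. The operational rule is: "TLP is defined as the interval following the index procedure until a DUS assessment indicates that the target lesion(s) is no longer patent". Loss of patency is then specified as PSR of 2.5 or more in the treated segment. Revascularization is not mentioned.
- **SAP 1.C, item 1.** TLR is a separate secondary endpoint, the interval "until the first revascularization procedure (e.g. PTA, cryoplasty, etc.) of the target lesion". The examples for target vessel revascularization (TVR) run "e.g. PTA, stenting, surgical bypass, etc.) in the target vessel"; surgical bypass is named only there.
- **SAP 1.C, TLP items.** Item 8 is headed "Primary TLP (Sustained and Expanded) for Target Lesion Lengths" above 160 mm. Items 17 and 18 cover sustained and expanded TLP. Item 19 is "Cumulative (primary-assisted and secondary) TLP". None of them states a TLR condition, and neither primary-assisted nor secondary is defined.
- **SAP 1.C, items 15 and 16.** Sustained hemodynamic and clinical success do carry such a condition: "without the need for repeated TLR in surviving subjects".
- **SAP 2.C, Sample Size Determination.** TLP failure was 18% in RESILIENT, and the same adjusted rate is expected here. Assumption 8 reads "The censoring rate through 12-months post-index procedure will be 15" percent; what censors a subject is not stated.
- **SAP 1, Study Endpoints.** The primary endpoints, freedom from TLR/TVR and secondary device success "will be compared to the RESILIENT trial results (historical control").
- **Time and Events Schedule.** DUS falls at 30 days, 12 months, and 24 and 36 months.

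**The concern.** The definition and the name of the endpoint disagree. Calling the endpoint primary TLP, and listing primary-assisted and secondary TLP separately, implies that re-treating the lesion ends primary patency. The defining sentence lets only a failing scan end it. A lesion that narrowed, was re-treated and was then found open at 12 months would therefore count as a patency success.

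The primary effectiveness result is at stake, because TLP is its chronic half. The text leaves three scorings open for such a subject: success (literal reading), failure (TLR as an event), or censored. They give different 12-month rates, and the choice should not be open once the data have been seen.

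**Working it through.** **1. The plan's own figures.** These reproduce and are not in dispute.

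- RESILIENT device success: 100 − 10 − 18 = 72%.
- Expected CONTINUUM device success: 100 − 1 − 18 = 81%.
- Censoring: 140 / 0.85 = 164.7, so 165. Conversely, 15% of 165 is 24.75, leaving 140.25.

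**2. One subject under the literal rule.** The stent is delivered successfully. The 30-day DUS shows PSR below 2.5. TLR is done at, say, month 6 without a failing DUS beforehand. The 12-month DUS shows PSR below 2.5. No DUS has shown PSR of 2.5 or more, so the TLP interval has not ended: the lesion is primary-patent and the subject is a device success. The same subject fails freedom from TLR. An unscheduled failing DUS before the TLR would have been an event, so the gap covers only subjects without one. No scan is scheduled between 30 days and 12 months to provide it.

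**3. Size.** Let x be the percentage of all subjects who are re-treated without an earlier failing DUS, open at 12 months and otherwise successes. The documents give no value for x; 1, 2 and 4 are assumptions. They also do not say whether the 18% counts TLR, so both cases are shown.

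| x (assumed) | Literal rule, if the 18% counts TLR: 81 + x | TLR as event, if the 18% is DUS-only: 81 − x | Subjects per 140 | Subjects per 234 |
|---|---|---|---|---|
| 1% | 82% | 80% | 1.4 | 2.3 |
| 2% | 83% | 79% | 2.8 | 4.7 |
| 4% | 85% | 77% | 5.6 | 9.4 |

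The gap between the two rules is x points in either case. The 140 are evaluable subjects and the 234 are enrolled. Applying 15% censoring to 234 leaves 234 × 0.85 = 198.9, so 1% of evaluable subjects would be about 2.0.

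**4. Why censoring at TLR does not solve it.** Suppose the 18% counts TLR, re-treatments occur before the 12-month scan, and all other failures are found at that scan. TLP with TLR as an event is then 82.0%. Kaplan-Meier with censoring at TLR gives 1 − (18 − x)/(100 − x):

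- x = 1: 1 − 17/99 = 82.8% (literal rule 83%)
- x = 2: 1 − 16/98 = 83.7% (literal rule 84%)
- x = 4: 1 − 14/96 = 85.4% (literal rule 86%)

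Censoring removes little of the difference.

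**5. The RESILIENT comparison.** If both studies ignore TLR, or both count it, the rule itself creates no mismatch. If RESILIENT counted TLR and CONTINUUM does not, x points enter the comparison: x/7.5 = 13%, 27% or 53% of the non-inferiority margin. To illustrate x = 2 under that assumption, use a simple unpooled comparison of proportions (not the planned Cox model) with 112 and 140 subjects. At the margin, true CONTINUUM success is 72 − 7.5 = 64.5%, reported as 66.5%. The standard error is √(0.72 × 0.28/112 + 0.665 × 0.335/140) = 0.0582. The chance of declaring non-inferiority is Φ(0.02/0.0582 − 1.645) = Φ(−1.30), or 9.7% instead of 5%.

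**The case against.** The strongest reply is that the label already settles the matter. If primary is read against item 19, re-treatment ends primary patency, and the literal reading leaves primary-assisted TLP little to describe. Items 15 and 16 needed a TLR clause because their names carry no such contrast. If the label carries no meaning, the plan simply has a DUS-measured endpoint with TLR reported alongside, and adding TLR is a design preference.

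The first half is good evidence of intent, but it does not supply a rule. The plan gives TLP an explicit operational definition, and that definition produces the result in step 2. The second half would require the plan to drop the contrast it makes between primary and assisted patency.

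Several narrower points stand:

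- The affected group is narrow, and its size cannot be taken from the documents. The table restates an assumed x.
- Bias against RESILIENT is conditional. Nothing in the documents shows that its 18% was scored differently.
- The 15% is a sample-size assumption, not a censoring rule. It shows only that the text is silent on what censors a subject.
- Freedom from TLR/TVR is reported and compared with RESILIENT separately, so re-treatment stays visible, although this does not correct TLP.
- Only a protocol summary is available here. The full protocol may contain the missing rule.
- The TLR examples are open-ended, so bypass is not excluded. That question is secondary.

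**Conclusion.** The concern holds. As written, a re-treated lesion can be scored primary-patent and its subject a device success, contrary to what the endpoint's name implies. Against a definition that counts TLR, 12-month patency and device success are overstated by one point for each 1% of subjects affected. The actual size is unknown.

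Confidence is high that the supplied text lacks the rule and that the literal reading has this effect. Any effect on the RESILIENT comparison depends on that trial having used a different rule, which the documents do not state. The point should be fixed because it concerns the event definition of the primary effectiveness endpoint and is cheap to settle in advance.

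**What to change.** In SAP 1.B:

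1. Define loss of primary TLP as the earlier of a DUS with PSR of 2.5 or more (or documented occlusion) or any TLR.
2. State that TLR is an event on its own date and not a censoring time.

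In SAP 1.C:

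3. Define primary-assisted and secondary TLP, and let only those (item 19) continue past re-intervention. Apply the same TLR rule to items 8, 17 and 18 at their respective PSR thresholds.
4. State whether surgical bypass of the target lesion counts as TLR.

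For the historical comparison:

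5. Score RESILIENT TLP by the same rule, or disclose how its 18% was scored.

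The cost is mainly wording, because TLR and DUS data are already collected. The reported patency rate may be slightly less favourable. The bypass clarification also touches the freedom from TLR/TVR endpoint. If RESILIENT was scored differently, its data may need rescoring, or the difference must be reported as a limitation of the comparison.

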#### C. Secondary Endpoints

1. **Freedom from TLR and/or TVR** through 12-months post-index procedure. TLR is defined as the interval following the index procedure until the first revascularization procedure (e.g. PTA, cryoplasty, etc.) of the target lesion. TVR is defined as the interval following the index procedure until the first revascularization procedure (e.g. PTA, stenting, surgical bypass, etc.) in the target vessel.
2. **Secondary Device Success** (compared to RESILIENT LifeStent®).
3. **Primary Safety** (freedom from occurrence of death at 30-days and 12-months post-index procedure) of the *Target Lesion Lengths > 160 mm* subgroup compared to the *Target Lesions treated with the 200 mm LifeStent®* subgroup.
4. **Primary Safety** (freedom from occurrence of death at 30-days and 12-months post-index procedure) of the following subgroups: 1) *Target Lesion Lengths  $\leq 160$  mm*, 2) *Target Lesion Lengths > 160 mm and  $\leq 240$  mm*, and 3) *Target Lesions treated with the 200 mm LifeStent®*.
5. **Primary Effectiveness** (Device Success) of *Target Lesion Lengths > 160 mm* subgroup compared to the *Target Lesions treated with the 200 mm LifeStent®* subgroup.

6. **Primary Effectiveness** (Device Success) of the following subgroups: 1) *Target Lesion Lengths  $\leq 160$  mm*, 2) *Target Lesion Lengths  $> 160$  mm and  $\leq 240$  mm*, and 3) *Target Lesions treated with the 200 mm LifeStent®*.
7. **Freedom from Fracture** (FFF) at 12- and 24-months post-index procedure.
8. **Primary TLP (Sustained and Expanded) for Target Lesion Lengths  $> 160$  mm** at 12, 24- and 36-months post-index procedure corresponding to PSR values of  $< 2.0$ ,  $< 2.5$ , and  $< 3.0$ .
9. **Freedom from TLR and/or TVR for Target Lesion Lengths  $> 160$  mm** at 12-, 24-, and 36-months post-index procedure.
10. **Secondary Safety** defined as freedom from death (excluding 30-days and 12-months post-index procedure), stroke, MI, emergent surgical revascularization, significant distal embolization in target limb, target limb major amputation, and thrombosis of target vessel at 30-days and 12-, 24-, and 36-months post-index procedure.
11. **Acute Technical Success** defined as successful deployment of the stent to the intended location.
12. **Acute Lesion Success** defined as attainment of  $\leq 30\%$  residual stenosis of the target lesion using any percutaneous method and/or non-investigational device (i.e., post-dilatation).
13. **Acute Procedure Success** defined as lesion success and no peri-procedural complications (death, stroke, MI, emergent surgical revascularization, significant distal embolization in target limb, and thrombosis of target vessel).
14. **Sustained Freedom from TLR and/or TVR** at 24- and 36-months post-index procedure.
15. **Sustained Hemodynamic Success** defined as sustained improvement of Ankle-Brachial Index (ABI) from baseline value of  $\geq 0.15$  at 30-days and 12-, 24-, and 36-months post-index procedure without the need for repeated TLR in surviving subjects.
16. **Sustained Clinical Success** defined as sustained cumulative improvement from baseline value of  $\geq 1$  category according to Rutherford et al. at 30-days and 12-, 24-, and 36-months post-index procedure without the need for repeated TLR in surviving subjects.
17. **Sustained TLP** at 24- and 36-months post-index procedure corresponding to PSR  $< 2.5$ .
18. **Expanded TLP** at 12-, 24- and 36-months post-index procedure corresponding to PSR  $< 3.0$ .
19. **Cumulative (primary-assisted and secondary) TLP** at 12-, 24-, and 36-months post-index procedure corresponding to PSR  $< 2.5$  and PSR  $< 3.0$ .
20. **Quality of Life** as assessed by Walking Impairment Questionnaire (WIQ) at baseline, 30-days and 12-, 24- and 36-months post-index procedure.

